The Effect of Intestinal Microbiota Transplantation for Inflammatory Bowel Diseases (IBD)

Date: 2017.05

1.Method

Intestinal microbiota transplantation(IMT) refers to make fecal from the health into a suspension of microbes through an intelligent bacteria processing system, and then infuse the suspension into the gastrointestinal tract of patients through naso intestinal tube, gastroscope, enteroscope or capsule intake which can reconstruct intestinal microbiota and play the role of treatment without obvious side effect.

2.Plan

1)Patient recruitment

Inclusion Criteria:

- Standard or conventional medicine treatment ineffective of Inflammatory Bowel Diseases(IBD) patients
- IBD patients with recurrent symptoms
- IBD patients who had drug dependence or recurrence when reduced or discontinued use
- Untreated IBD patients who voluntarily received Standardized Intestinal Microbiota Transplantation(IMT)
- Written informed consent/assent as appropriate

Exclusion Criteria:

- IBD patients with contraindications for gastrointestinal endoscopy
- IBD patients with indication of surgery
- Moderate and severe renal injury(serum creatinine>2mg/dL or 177mmol/L), moderate and severe chronic obstructive pulmonary disease, severe hypertension, cerebrovascular accident, congestive heart failure, unstable angina pectoris
- Other serious diseases that may interfere the recruitment or affect the survival, such as cancer or acquired immune deficiency syndrome
- Mentally or legally disabled person
- Preparing for pregnancy
- Medical or social condition which in the opinion of the principal investigator would interfere with or prevent regular follow up
- Participating in other clinical trials.

Recruit the patients who meet the inclusion criteria, and fail to meet the exclusion criteria. Introduce this clinical trial to the patients and obtain the informed consent. Assess the condition of the disease.

2)Arms and Interventions

Randomly divided the patients into experimental arm and control arm and

intervene them as described in the following table.

arms	Assigned interventions

Experimental: Standardized IMT 30 patients with inflammatory bowel disease ongoing traditional drugs will be recruited for the study, which taking intestinal microbiota transplant three times a week.
 
Interventions:
 
Procedure: Intestinal Microbiota Transplantation
 
Procedure: traditional drugs
	
intestinal microbiota transplant
 
Participants in Experimental group take IMT three times a week.
 
Drug: traditional drugs such as Mesalazine\glucocorticoid, All participants continue his or her therapy.

Traditional drugs 30 patients with inflammatory bowel disease ongoing traditional drugs will be recruited for the study
 
Interventions:
 
Procedure: traditional drugs such as Mesalazine\glucocorticoid
	
Drug: Mesalazine\glucocorticoid
 
All participants continue his or her therapy.

3) Outcome Measures

Primary Outcome Measure:

The change of the modified Mayo score

Clinical remission defined as modified Mayo score ≤ 2 . Change from baseline will

be assessed at different time point. The endpoint of follow-up is the time of clinical recurrence.

[Time Frame: 1 month, 3 months, 6months, 12 months]

Secondary Outcome Measure:

① The change of CDAI

Clinical remission defined as CDAI (Crohn's disease activity index) ≤ 150 . Change from baseline will be assessed at different time point. The

endpoint of follow-up is the time of clinical recurrence.

[Time Frame: 1 month, 3 months, 6months, 12 months]

② Relief of gastrointestinal symptoms

The onset and duration of gastrointestinal symptoms will be assessed by

"Evaluation Score Table of Gastrointestinal Symptoms". Change from

baseline

will be assessed at different time point.

[Time Frame: 1 month, 3 months, 6months, 12 months]

③ Changes of gut microbiota

Alpha and Beta diversity of GI microbiota by High-throughput sequencing on

baseline line and 1 month, 3 months, 6months, 12 months after treatment.

[Time Frame: 1 month, 3 months, 6months]

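### The fourth inclusion criterion ties entry to receiving or choosing IMT, which does not fit random allocation, and no eligibility rule covers earlier IMT

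*Protocol*

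**What the plan says.** Under Protocol section 2, Patient recruitment, the fourth inclusion criterion admits "Untreated IBD patients who voluntarily received Standardized Intestinal Microbiota Transplantation(IMT"). The same section applies eligibility first: "Recruit the patients who meet the inclusion criteria, and fail to meet the exclusion criteria". The next section, Arms and Interventions, then states: "Randomly divided the patients into experimental arm and control arm".

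The arms table describes the two groups as follows.

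- Experimental: "Experimental: Standardized IMT 30 patients with inflammatory bowel disease ongoing traditional drugs will be recruited for the study", with IMT added to the drugs.
- Control: "Traditional drugs 30 patients with inflammatory bowel disease ongoing traditional drugs will be recruited for the study". The only intervention listed is the existing drug treatment: "All participants continue his or her therapy". No sham procedure is described.

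There are eight exclusion criteria. The one closest to previous treatment is "Participating in other clinical trials". None mentions earlier IMT or an IMT-free interval before baseline.

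**The concern.** An inclusion criterion should describe patients before, and independently of, the treatment they will be assigned. This one describes them by the experimental treatment itself, either as something already received or as something they have chosen. Both sit badly with a design in which chance decides who gets IMT.

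The trial compares IMT plus drugs with drugs alone, in 30 patients per arm followed to 12 months. Two things are at stake. The first is what baseline means: the clinical outcomes are changes from baseline, and microbiota diversity is also measured at baseline. The second is whether the control arm stays in the trial, and stays free of IMT, for the whole of follow-up.

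**Working it through.** The protocol gives no effect size, power or contamination rate, so there is no figure to reproduce. The main check compares the wording.

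**1. How the criteria combine.** The first three inclusion criteria concern patients whose treatment has failed, whose symptoms recur, or who depend on drugs. The fourth concerns untreated patients. One patient can hardly meet all four, so I take them as alternatives, with consent required of everyone. A patient can then enter on the fourth criterion alone and be allocated to either arm.

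**2. Literal reading: IMT already received.** Such a patient is eligible, and no exclusion removes them. The exclusion about other trials is in the present tense, so it misses IMT given as care or in a completed trial. The gap does not depend on the fourth criterion: patients entering under the first three could also have had IMT before.

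The effect on the comparison can be written down. Let q be the share with earlier IMT. It is the same in both arms in expectation, because the exposure precedes randomisation. Let δ be the added effect of trial IMT in patients without earlier exposure, and δ′ the added effect in those with it. Then

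expected arm difference = (1 − q)·δ + q·δ′.

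- If δ′ = δ, the difference is unchanged.
- If δ′ = 0, because an earlier full effect persists, it is (1 − q)·δ.
- If an earlier effect wanes in controls during follow-up, δ′ can exceed δ.

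Earlier exposure therefore changes whose effect is estimated, in a direction the document does not determine. It does not by itself bias the randomised comparison. It does mean that some baseline scores and microbiota samples would be taken after IMT.

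**3. Likelier reading: volunteering to receive IMT.** The criterion then selects patients who want IMT, and random allocation sends some of them to drugs alone. With no sham described, they can tell that they did not receive it. They may withdraw, or obtain IMT elsewhere, more often than patients without that preference.

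**4. Illustrative size for IMT obtained by controls after randomisation.** Let p be the share of controls who obtain it and gain the full effect, with patients analysed as allocated. The expected difference is multiplied by (1 − p):

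- p = 3/30: 0.90
- p = 6/30: 0.80
- p = 9/30: 0.70

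Power, by normal approximation with 30 per arm and two-sided 0.05, is Φ(d·(1 − p)·√(30/2) − 1.96), where d is the true standardised difference. Both d and p are assumptions.

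| d | p = 0 | p = 10% | p = 20% | p = 30% |
|---|---|---|---|---|
| 0.50 | 49% | 41% | 34% | 27% |
| 0.72 | 80% | 71% | 61% | 50% |
| 1.00 | 97% | 94% | 87% | 77% |

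The middle row is the difference that 30 per arm would detect with 80% power: (1.96 + 0.84)·√(2/30) = 0.72.

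**5. A related conflict in the same criterion.** The criterion speaks of untreated patients, yet the arms table defines both arms by ongoing traditional drugs that are to be continued. An untreated patient fits neither description.

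**The case against.** The strongest reply is that this is loose English. A patient who has had IMT for the disease is hardly untreated, so the clause most plausibly means volunteering to receive IMT. Anyone entering a trial with an IMT arm must be willing to receive it, and written consent is already required. That stands as to the likelier intent. It does not rescue the clause: willingness to have IMT is not willingness to be allocated to either arm, and an eligibility rule is applied as written.

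A reader might infer that patients are promised IMT and that allocation breaks the promise. The text contains no such promise. The protocol has the trial introduced and consent obtained before it describes allocation, and the consent pages are not in the copy reviewed.

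A reader might also infer that earlier IMT carries over into the control arm and pulls the result towards zero by (1 − p). The document does not support this. Earlier exposure falls on both arms in expectation, benefit already gained is inside the baseline of a change score, and waning in controls would act the other way.

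An open control arm can disappoint patients under any criterion, and that is true. This criterion adds to the problem by selecting on the preference.

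**Conclusion.** The point holds in a limited form. What is certain is the wording: eligibility is tied to receiving or choosing the tested treatment, allocation is said to be random, and no criterion deals with earlier IMT. What is uncertain is how often it matters. The protocol gives no rate of earlier IMT, of withdrawal by preference, or of IMT obtained elsewhere.

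The (1 − p) and power figures apply only to IMT obtained by controls after randomisation, under an assumed p and a full effect. They show how little room a trial of 60 has and are not evidence of an established bias. It would go too far to conclude that the comparison is biased whichever way the criterion is read. Earlier exposure threatens clean baselines and a clear contrast, whereas bias could arise from preference-related withdrawal or outside IMT. The wording should be corrected before recruitment relies on it.

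**What to change.** - Delete the IMT clause from the fourth inclusion criterion, and require every patient to be willing to be allocated to either arm.
- Add an eligibility rule on earlier IMT that applies under all criteria. It could be an exclusion, or an IMT-free interval before baseline chosen by the sponsor. The document does not settle which, and a lifetime bar is only one option.
- Record any IMT obtained outside the trial during the 12 months, and analyse patients in their allocated arm. The analysis rule may already stand in a statistical analysis plan that is not shown; the recording belongs in the protocol.
- In the same edit, reconcile the reference to untreated patients with the arms table, which describes both arms as on ongoing drugs.

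The cost is protocol wording, one screening question, and the loss of a few patients who have had IMT or would accept only IMT.

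### Randomisation names no stratum for disease type, although the activity indices are disease-specific, so the disease split between arms is left to chance; stratifying is a cheap improvement of modest size

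*Protocol*

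**What the plan says.** Under Arms and Interventions, the allocation rule is one sentence: "Randomly divided the patients into experimental arm and control arm". The arms table then gives the sizes: "Experimental: Standardized IMT 30 patients with inflammatory bowel disease ongoing traditional drugs will be recruited for the study" and "Traditional drugs 30 patients with inflammatory bowel disease ongoing traditional drugs will be recruited for the study". Neither entry divides the 30 by disease type. The inclusion criteria also treat the disease as one group, for example "Standard or conventional medicine treatment ineffective of Inflammatory Bowel Diseases(IBD) patients". No stratification factor, block scheme, minimisation factor or disease quota appears anywhere.

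Under Outcome Measures, the primary outcome is "The change of the modified Mayo score", with "Clinical remission defined as modified Mayo score ≤ 2". The first secondary outcome has its own index and cut-off: "Clinical remission defined as CDAI (Crohn's disease activity index) ≤ 150". The second, "Relief of gastrointestinal symptoms", and the third, gut microbiota diversity, are not restricted to either disease. Under Patient recruitment, the patient's disease is assessed before the step at which arms are assigned.

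**The concern.** Two activity indices with separate remission cut-offs make sense only if two diseases are enrolled. Each clinical index, including the primary one, is then informed by part of the sample, while the symptom and microbiota outcomes combine both parts. A random division into 30 and 30 balances the totals but not the number of patients with each disease in each arm.

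Two things are at stake. First, the subset behind the Mayo result, or behind the CDAI result, may split unevenly, which costs precision. Second, a chance difference in disease mix adds variability to an unadjusted comparison of the pooled outcomes if the two diseases change by different amounts. Disease type can be known before allocation, so both can be largely prevented by design. An analysis plan can add a covariate later, but it cannot alter an allocation already made.

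**Working it through.** **Inputs.** From the protocol: 30 patients per arm, 60 in total. Assumed, because the protocol does not give it: K, the number of the 60 with the Mayo-scored disease, varied from 12 to 48. Also assumed: arm totals held at exactly 30/30, two-sided alpha of 0.05, and a normal approximation for two means. The figure of 30 per arm cannot be reproduced, since no effect size, SD, power or alpha is stated.

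**1. Chance split.** With arms fixed at 30, the number of Mayo-disease patients in one arm is hypergeometric (60, K, 30), with variance 30·(K/60)·(1−K/60)·(30/59). A difference of six patients between arms is 6/30 = 20 percentage points of disease mix.

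| K | SD of count in one arm | 95% range in one arm | P(difference ≥ 6) | P(difference ≥ 8) |
|---|---|---|---|---|
| 12 | 1.56 | 3 to 9 | 10.4% | 2.1% |
| 20 | 1.84 | 6 to 14 | 17.0% | 5.4% |
| 30 | 1.95 | 11 to 19 | 19.6% | 7.0% |
| 40 | 1.84 | 16 to 24 | 17.0% | 5.4% |
| 48 | 1.56 | 21 to 27 | 10.4% | 2.1% |

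If arm totals were not held fixed (simple randomisation), the chance of a difference of six or more would run from 15% at K = 12 to 47% at K = 48. Part of that is unequal arm totals rather than unequal mix, and the protocol states 30 per arm, so the conclusion does not rest on it.

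**2. Precision of the Mayo comparison.** For a split a/b with a + b = K, the variance relative to an even split is (1/a + 1/b)/(4/K).

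- 18/12: (1/18 + 1/12)/(4/30) = 1.042, or +4% (about +2% in standard error).
- 19/11: 1.077, or +8%.
- 13/7: (1/13 + 1/7)/(4/20) = 1.099, or +10%.
- 14/6: 1.190, or +19% (about +9% in standard error).

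Take an effect that gives 80% power at an even split, which is (1.96 + 0.84)·√(4/K) SD. Average power over all chance splits is then 78.6% at K = 20, 79.3% at K = 30 and 79.7% at K = 40. The loss is larger for a very small subset: the same formula gives 76.9% at K = 12. Single bad draws cost more, such as 75.2% at 20/10 and 67.9% at 15/5, but a split of 15/5 or worse has a chance of only 1.3% at K = 20.

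**3. Pooled outcomes.** The between-arm difference in disease share has SD 2·SD(count)/30:

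- K = 20 or 40: 2·1.84/30 = 0.123.
- K = 30: 2·1.95/30 = 0.130.

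With 30 per arm and a within-disease SD of 1, the standard error is √(2/30) = 0.258. Suppose change scores differ between the diseases by g within-disease SD (assumed 0.5 to 1.0). An unadjusted comparison then has standard error √(2/30 + (g·SD of share difference)²):

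- g = 0.5, K = 20: √(0.0667 + 0.0038) = 0.265.
- g = 1.0, K = 30: √(0.0667 + 0.0170) = 0.289.

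This is an increase of about 3% to 12% in standard error. At K = 12 or 48 the SD of the share difference is 2·1.56/30 = 0.104, and the range is a little lower, 0.263 to 0.278.

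**The case against.** The strongest reply is that the protocol is silent on stratification and does not state that allocation is unstratified; a fuller randomisation procedure may sit in a document not shown. That is fair as to certainty. But allocation is something a protocol can be expected to fix, and the rule it gives contains no factor.

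The second reply is that the gain is small. This stands. The losses on the Mayo subset are a few per cent of variance in most draws, and about one power point on average unless the subset is very small.

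The third concerns the pooled outcomes, and it also largely stands. The outcomes are changes from baseline, so stable differences in level between the diseases largely cancel; only a difference in change matters, and the 0.5 to 1.0 SD used here is an assumption. A disease-type term would recover most of the loss even without stratification. With 18 against 12 Mayo-disease patients in arms of 30, the correlation between arm and disease is 0.2, and adjustment costs only 1/(1 − 0.04), about +4% variance. Whether that term is planned belongs to the analysis plan, so its absence here is not an omission. What adjustment cannot do is refill a thin arm within one disease.

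Three stronger readings should be resisted:

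- A reader might infer that the comparison is biased. It is not: random allocation stays unbiased, overall and within each disease.
- A reader might infer that chance imbalance adds error on top of the ordinary standard error. If the outcome SD is the pooled SD, it already contains the between-disease variance, and the ordinary standard error already covers the imbalance. The increase above applies only relative to the within-disease SD.
- A reader might infer a weakness in allocation concealment from the brevity of the sentence. Nothing in the document establishes one.

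**Conclusion.** The point holds as a cheap improvement of modest size, for the sponsor to consider. The stated allocation rule leaves the disease split between arms to chance, with a roughly 10% to 20% probability of a difference of six or more patients over the assumed disease mixes and fixed 30/30 totals. The consequence is some loss of precision, not bias. On the Mayo subset it averages about 1.5 power points or less from K = 20 upward and about 3 points at K = 12. On the pooled outcomes, at K = 20 to 40, it is at most about 12% in an unadjusted standard error, and that upper end needs the two diseases to differ by a full SD in change.

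All figures depend on an assumed disease mix. The link between the Mayo score and ulcerative colitis is general knowledge; the protocol never names that disease, though it ties CDAI to Crohn's disease itself. It would go too far to say that stratification secures the primary outcome. It balances the arms within each disease but does not determine how many patients carry the Mayo score, which is a separate and larger question.

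**What to change.** Replace the allocation sentence with: *Disease type (ulcerative colitis or Crohn's disease) is recorded before allocation, and patients are randomised 1:1 to the two arms separately within each disease type, using permuted blocks.* Include disease type as a term in the analyses of the gastrointestinal symptom score and the microbiota outcomes.

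With this change each disease divides about evenly, to within about half a block. For K = 30 that means about 15/15 in each disease, instead of a 95% range of 11 to 19 in one arm. The cost is two randomisation lists instead of one, one model term, and arm totals that may miss 30/30 by one or two. No extra patients are needed.

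### Change in modified Mayo (primary) and CDAI is timed to 12 months, but an undefined recurrence sentence leaves open whether index scoring stops at recurrence

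*Protocol*

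**What the plan says.** All of this is in the protocol, section 2 (Plan), part 3 (Outcome Measures).

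- The primary outcome is headed "The change of the modified Mayo score", with "Time Frame: 1 month, 3 months, 6months, 12 months".
- The only disease state given a threshold there is remission: "Clinical remission defined as modified Mayo score ≤ 2".
- The same paragraph then says "The endpoint of follow-up is the time of clinical recurrence".
- The first secondary outcome, change in CDAI, has the same four time points, its own remission threshold (150 or below) and the same sentence: "endpoint of follow-up is the time of clinical recurrence".
- The second secondary outcome, gastrointestinal symptoms ("The onset and duration of gastrointestinal symptoms will be assessed by" a score table), also runs to 12 months but carries no such sentence.

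No score, rise in score, symptom or treatment criterion defines recurrence. The word also appears in the inclusion criteria, again without a definition. The protocol does not say whether Mayo or CDAI is scored at the remaining visits after recurrence, or whether the score at recurrence is itself recorded.

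**The concern.** A change score at fixed months needs a score at each of those months. A rule that ends follow-up at recurrence removes scores from exactly the patients who have done badly after doing well. Those who remain at month 12 have been selected by their outcome, so comparing them by arm is no longer a comparison of the randomised groups.

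This is a rule about data collection, which sites apply visit by visit. A statistical analysis plan can choose how to model scores that were not collected, but it cannot recover them. The point is therefore not that a missing-data method is absent from the protocol. It is that the protocol contains a sentence which, followed as written, creates the gap in its own primary outcome.

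**Working it through.** **Text check.** The sentence has two readings.

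1. Literal: follow-up of the index ends at recurrence. The 3, 6 and 12 month scores then exist only for patients who have not yet recurred.
2. Event: recurrence is something to be watched for. All scores are then collected, but time to recurrence is a different variable from the change score and is not listed as an outcome.

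The 12-month time frame does not decide between them. It could mean visits for everyone, or a maximum for those still free of recurrence. Taking recurrence to be loss of remission (Mayo above 2, CDAI above 150) is not written, and it gives no rule for a patient who never remits.

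**Illustration of the literal reading.** The protocol has no figure to reproduce: it gives no remission rate, recurrence rate, effect or SD. Everything below is assumed.

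- Relapsers are a subset of remitters.
- Month-12 change is -4 in sustained remission and 0 in everyone else. Negative differences (IMT minus control) favour IMT.
- s = proportion in sustained remission = remitters minus relapsers; r = proportion relapsing by month 12.
- Relapses are first seen one third each at months 3, 6 and 12.

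Formulas for each arm's month-12 mean:

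- True: -4s
- Followed, recurrence-visit score discarded: -4s / (1 - r)
- Followed, recurrence-visit score kept: -4s / (1 - r + r/3), because the third first seen to relapse at month 12 still have a score

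Case A: 60% remit in both arms; 30% of controls and 10% of IMT patients relapse, so s = 0.30 and 0.50.

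Case B: 50% of controls and 70% of IMT patients remit; 10% and 30% relapse, so s = 0.40 in both arms.

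| | Control | IMT | Difference |
|---|---|---|---|
| A, true | -1.20 | -2.00 | -0.80 |
| A, score discarded | -1.2/0.7 = -1.71 | -2.0/0.9 = -2.22 | -0.51 |
| A, score kept | -1.2/0.8 = -1.50 | -2.0/0.933 = -2.14 | -0.64 |
| B, true | -1.60 | -1.60 | 0 |
| B, score discarded | -1.6/0.9 = -1.78 | -1.6/0.7 = -2.29 | -0.51 |
| B, score kept | -1.6/0.933 = -1.71 | -1.6/0.8 = -2.00 | -0.29 |

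Swapping the arms in Case B reverses the sign: +0.51 or +0.29. The expected differences do not depend on the number of patients.

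**Sensitivity to the assumed rates (score discarded).**

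- Case B with a smaller gap (s = 0.40 in both arms, control relapse 10%): IMT relapse of 20% gives -1.6/0.8 + 1.6/0.9 = -0.22; 15% gives -1.6/0.85 + 1.6/0.9 = -0.10.
- Relapse of 20% in both arms with equal remission: no bias.
- Relapse of 20% in both arms with remission of 70% on IMT and 50% on control: true -2.0 + 1.2 = -0.80, shown -0.80/0.8 = -1.00.

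**Does a likelihood-based analysis repair it?** A multivariate normal model was fitted to simulated data: arm-specific visit means, common unstructured covariance, patient and visit SDs of 1.06 each, and 60,000 patients per arm to show the limit. At month 12:

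- Recurrence score kept: -0.59 in Case A and -0.22 in Case B, against -0.64 and -0.29 for the simple followed-only comparison. Case B improves; Case A moves slightly further from -0.80.
- Recurrence score not recorded: -0.04 and -0.76, against -0.51 and -0.51. Both are further from the truth.

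Such an analysis therefore cannot be relied on to remove the bias in these cases.

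**The case against.** The strongest reply is that the sentence never says visits stop or that a patient leaves the study, and that the four time points are listed directly below it without exception. If recurrence is simply an event to be watched for, no score is lost and none of the bias figures apply. That stands as a possible reading, but the text does not establish it, and it leaves an event variable that is undefined and unlisted.

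A reader might infer that the primary variable itself is in doubt. The document does not support that: the heading names the change in modified Mayo score. A reader might also take -0.51 as the expected distortion, or as a tilt towards IMT. Neither follows. The rates are assumed, -0.51 is the case with the recurrence-visit score discarded, Case A understates IMT, and swapping the arms in Case B reverses the sign.

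It is also fair to say that an analysis rule setting change to 0 after recurrence would recover the truth in this illustration without any later scores. It does so because the illustration fixes relapsers at 0. If relapsed patients later move away from 0, only observed scores can show it. The analysis plan is not shown and may contain such a rule, but that rule would still be an assumption about scores not collected.

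**Conclusion.** The point holds in a limited form and should be fixed; confidence is moderate. The conflict in the text needs no assumption: the protocol fixes change scores to 12 months, ends follow-up at an undefined event under the same two outcomes, and does not say whether scoring continues.

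The bias is conditional. It arises only if scoring really stops at recurrence and recurrence or remission differs by arm. It can go either way and is absent when both are equal. In the two main assumed cases it is 0.29 and 0.51 points with the recurrence score discarded, and 0.16 and 0.29 points with it kept. The protocol gives nothing from which to say what it would be in this trial, and it does not show that relapsed patients will in fact go unscored.

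**What to change.** Under both the modified Mayo and the CDAI outcome, replace the recurrence sentence with a statement that the index is scored for every randomised patient at 1, 3, 6 and 12 months whether or not recurrence has occurred. If recurrence is of interest, define it and list time to recurrence as a separate secondary outcome, so that the intended recurrence follow-up is kept.

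How scores still missing are analysed, and how patients who never remit are handled, can be left to the statistical analysis plan. Which index applies to which patient is a separate question.

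The cost is a wording change plus index scoring of relapsed patients at time points already listed; the symptom outcome already runs to 12 months without a recurrence stop. The exact added burden cannot be stated, because the components of the modified Mayo score are not given.
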